6.4.10. Safety Assessments

6.4.10.1. Columbia-Suicide Severity Rating Scale

The C-SSRS is a tool designed to systematically assess and track suicidal AEs (suicidal behavior and suicidal ideation). The strength of this suicide classification system is in its ability to comprehensively identify suicidal events while limiting the over-identification of suicidal behavior. The C-SSRS Baseline/Screening Version will be used at V1 and the C-SSRS Since Last Visit Version will be used for subsequent visits. Assessments will be performed as specified in the Schedule of Study Procedures (Table 1). An example of the instrument is provided in Appendix 2.

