8.6. Safety Analyses

Safety data, including C-SSRS, will be descriptively summarized separately for OL phase and double-blind randomized withdrawal phase.

The OL phase data will be summarized for all subjects and by enrollment group (De Novo Group or 0169 Completers Group), and the double-blind randomized withdrawal phase data will be summarized by treatment group according to treatment subjects received. Quantitative data collected at unscheduled times will be listed but will not be included in summaries. Categorical data collected at unscheduled times (e.g., ECG finding categories) will not be included in summaries by time point but will be included in summaries of findings during the entire treatment period.

Safety analyses will be performed using the safety analysis set. Unless specified otherwise, there will be no imputation of missing data in safety summaries. Subjects without post baseline measurement (e.g. ECG or vital signs) for a given time point will be excluded from the summary statistic (e.g., denominator of the summary statistic) for that time point.

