
Interrupted Attempt: When the person is interrupted (by an outside circumstance) from starting the potentially self-injurious act (if not for that, actual attempt would have occurred). Overdose: Person has pills in hand but is stopped from ingesting. Once they ingest any pills, this becomes an attempt rather than an interrupted attempt. Shooting: Person has gun pointed toward self, gun is taken away by someone else, or is somehow prevented from pulling trigger. Once they pull the trigger, even if the gun fails to fire, it is an attempt. Jumping: Person is poised to jump, is grabbed and taken down from ledge. Hanging: Person has noose around neck but has not yet started to hang - is stopped from doing so. Has there been a time when you started to do something to end your life but someone or something stopped you before you actually did anything? If yes, describe:
	
Yes No  
 
Total # of interrupted _____

Aborted Attempt: When person begins to take steps toward making a suicide attempt, but stops themselves before they actually have engaged in any self-destructive behavior. Examples are similar to interrupted attempts, except that the individual stops him/herself, instead of being stopped by something else. Has there been a time when you started to do something to try to end your life but you stopped yourself before you actually did anything? If yes, describe:
	
Yes No   Total # of aborted _____

Preparatory Acts or Behavior: Acts or preparation towards imminently making a suicide attempt. This can include anything beyond a verbalization or thought, such as assembling a specific method (e.g., buying pills, purchasing a gun) or preparing for one's death by suicide (e.g., giving things away, writing a suicide note). Have you taken any steps towards making a suicide attempt or preparing to kill yourself (such as collecting pills, getting a gun, giving valuables away or writing a suicide note)? If yes, describe:
	
Yes No  

Suicidal Behavior: Suicidal behavior was present during the assessment period?
	
Yes No  

Suicide:
	
Yes No  

Answer for Actual Attempts Only
	
Most Lethal Attempt Date:

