RW Baseline	Last result prior to First Dose in RW Period [1]	
First Dose Day in RW Period (DD)		
Week 18 (Day 126) (DD+13)	First Dose in RW Period [1]	DD+20
Week 20 (Day 140) (DD+27)	DD+21	DD+34

Week 22 (Day 154) (DD+41)	DD+35	EOS
[REDACTED]		
[REDACTED]	[REDACTED]	
[REDACTED]	[REDACTED]	[REDACTED]
[REDACTED]	[REDACTED]	[REDACTED]
[REDACTED]	[REDACTED]	
[REDACTED]		
[REDACTED]	[REDACTED]	[REDACTED]
Safety laboratory test results (chemistry, hematology, and urinalysis)		
OL Baseline	Last result prior to first dose in OL Period	
Week 2 (Day 14)	2	34
Week 8 (Day 56)	35	83
Week 16 (Day 112)	84	First Dose in RW Period [1]
RW Baseline	Last result prior to First Dose in RW Period [1]	
First Dose Day in RW Period (DD)		
Week 22 (Day 154) (DD+41)	First Dose in RW Period [1]	EOS
ECGs		
OL Baseline	Last result prior to first dose in OL Period	
Week 4 Day 28	2	71
Week 16 (Day 112)	72	First Dose in RW Period [1]
RW Baseline	Last result prior to First Dose in RW Period [1]	
First Dose Day in RW Period (DD)		
Week 22 (Day 154) (DD+41)	First Dose in RW Period [1]	EOS

ABPM (collected in OL period only)		
Open-Label Baseline	Last results collected prior to first dose in OL Period	
Week 2 (Day 14)	2	23
Week 8 (Day 56)	24	OL Disposition Date

[1] First dose in RW period: When both a date and time are available for the first dose in the RW period and the assessment of interest, dates and times are used to determine the end of Analysis Week 16 (Day 112) and the beginning of the first applicable analysis week in the RW period, e.g. Analysis Week 18 (Day 126): An assessment is assigned to Analysis Week 16 (Day 112) if its date and time are prior to the date and time of the first dose in the RW period, and it is assigned to the first applicable analysis week in the RW period, e.g. Analysis Week 18 (Day 126) if it is on/after the date and time of the first dose in the RW period.

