9.7. Columbia-Suicide Severity Rating Scale (C-SSRS)

The C-SSRS is a tool designed to systematically assess and track suicidal AEs (suicidal behavior and suicidal ideation). The strength of this suicide classification system is in its ability to comprehensively identify suicidal events while limiting the overidentification of suicidal behavior. The C-SSRS Baseline/Screening Version is available at screening visit for De Novo subjects; the C-SSRS Since Last Visit Version is available for both rollover and De Novo subjects at subsequent visits. If the Since Last Visit Version of the C-SSRS is collected on the same day as the Baseline/Screening Version of the C-SSRS, the Since Last Visit Version of the C-SSRS does not have a valid reference and hence will be excluded from summarization and analysis. It will be included in the listing.

The following 11 C-SSRS categories include 5 subtypes of suicidal ideation (1–5), 5 subtypes of suicidal behavior (6–10), and self-injurious behavior without suicidal intent. They all have binary responses (yes/no).

- 1) Wish to Be Dead
- 2) Non-specific Active Suicidal Thoughts
- 3) Active Suicidal Ideation with Any Methods (Not Plan) without Intent to Act
- 4) Active Suicidal Ideation with Some Intent to Act, without Specific Plan
- 5) Active Suicidal Ideation with Specific Plan and Intent
- 6) Preparatory Acts or Behavior
- 7) Aborted Attempt
- 8) Interrupted Attempt
- 9) Actual Attempt (non-fatal)
- 10) Completed Suicide
- 11) Self-injurious Behavior Without Suicidal Intent

Counts and percentages will be presented for subjects in each C-SSRS category, as well as subjects with any suicidal ideation (1–5), subjects with any suicidal behavior (6–10), and subjects with any suicidal ideation or behavior (1–10), at each visit where the CSSRS was collected. The summary of the Baseline/Screening Version of the C-SSRS will present separately the assessment over the subject's lifetime and during the last 12 months. Only responses for De Novo subjects will be summarized, as the Baseline/Screening Version was administered in study 0169 for the rollover subjects.

10. [REDACTED]

■ [REDACTED]
[REDACTED]

■ [REDACTED]
[REDACTED]
[REDACTED]

■ [REDACTED]
[REDACTED]

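### C-SSRS is tabulated visit by visit from interval-specific forms, so no planned table counts the distinct subjects per arm with any suicidal ideation or behavior in the randomized withdrawal period

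*Protocol*

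**What the plan says.** Protocol 6.4.10.1 fixes the form: "The C-SSRS Baseline/Screening Version will be used at V1 and the C-SSRS Since Last Visit Version will be used for subsequent visits". The follow-up form in Appendix 2-8 has one response column, headed Since Last Visit, and its behavior section asks whether "Suicidal behavior was present during the assessment period". The same item stands in the Baseline/Screening form (Appendix 2-7), so it is the column heading and 6.4.10.1, not the item, that tie the answer to one interval.

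SAP 9.7 gives counts and percentages for eleven categories and three groupings, the last being "subjects with any suicidal ideation or behavior (1–10), at each visit where the CSSRS was collected". It mentions a listing, but no across-visit, worst-post-baseline or shift summary. On the lifetime and 12-month form it adds: "Only responses for De Novo subjects will be summarized, as the Baseline/Screening Version was administered in study 0169 for the rollover subjects".

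Which records enter the counts is set elsewhere in the SAP. Section 6 restricts summaries to data inside analysis windows unless noted otherwise. Section 6.5 assigns windows regardless of visit label. Section 6.5.1, as a general rule, keeps the record nearest the nominal time. With DD as the first randomized dose, the C-SSRS windows are Week 18 (to DD+20), Week 20 (DD+21 to DD+34) and Week 22 (from DD+35, nominal DD+41). Week 22 ends at EOS in Table 3 and at EOT in the second copy of the table in the same section.

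Protocol 8.6 says that categorical data from unscheduled times stay out of summaries by time point but "will be included in summaries of findings during the entire treatment period".

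**The concern.** For a scale that measures current status, a table by visit and one record per window are reasonable. The Since Last Visit form is different: each form reports events in its own interval, and the result for a period is the union of all the forms. Two things follow. Visit counts cannot be added up or otherwise turned into a number of subjects. And when the nearest-record rule sets a form aside, nothing else in the table covers that interval.

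C-SSRS is a named safety endpoint (protocol 3.4.3, SAP 3.2.4), and safety is one of the two primary objectives. If positive reports are few, a difference of one or two subjects between arms changes how the result reads, and that is the size of the ambiguity.

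**Working it through.** The plan states no figure on this point, so there is none to reproduce. The check has three parts.

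**1. What visit counts can tell.** Planned randomization is 154 at 1:1 (protocol 8.2 and 5.1), so 154 / 2 = 77 per arm. If the visits show c1, c2 and c3 positive subjects, the number of distinct subjects lies between max(c1, c2, c3) and min(c1 + c2 + c3, 77). The counts below are assumed, for illustration only.

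- 1, 1, 1: between 1 and 3 subjects; 1/77 = 1.3%, 3/77 = 3.9%.
- 2, 2, 2: between 2 and 6 subjects; 2/77 = 2.6%, 6/77 = 7.8%.

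These bounds cover only the forms that are kept. A discarded positive form can push the true number above the upper bound.

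**2. Which forms are discarded.** V9 is nominally DD+41. With the last dose on that day, V10 falls two weeks later, at about DD+41+14 = DD+55. The early-termination and unscheduled days below are assumed examples.

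| Form | Window | Days from nominal | Nearer record | In the table? |
|---|---|---|---|---|
| V10 at DD+55, window ending at EOS | Week 22 | 14 | V9, within 3 | No |
| V10 at DD+55, window ending at EOT | probably none | – | – | No, listed only |
| Early termination at DD+18 | Week 18 (nominal DD+13) | 5 | V7 at DD+13, 0 | No |
| Unscheduled at DD+24 | Week 20 (nominal DD+27) | 3 | V8 at DD+27, 0 | No |

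The EOT row assumes that EOT means end of treatment; neither abbreviation is in SAP Table 1. In the last row, if the rater counts from the unscheduled visit, the V8 form covers 27 − 24 = 3 days. The discarded form covers the other 24 − 13 = 11 days since V7.

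The loss is conditional. An early-termination form that is alone in its window is kept, and V10 stands in for Week 22 under the EOS version if no nearer record exists. The cases are still realistic. Protocol 6.4.10.12 allows any protocol assessment at unscheduled visits, C-SSRS is on the V10 procedure list, and SAP 8.4.1 provides for subjects who missed Week 6 because the sponsor ended the study.

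**3. Protocol 8.6 against SAP 9.7.** The protocol moves unscheduled categorical findings out of the by-visit tables and into whole-period summaries. SAP 9.7 contains only by-visit tables, so an unscheduled C-SSRS report has no whole-period summary to enter. SAP 11.2 does not list this as a change.

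**The case against.** The best reply is that nothing is lost. All scheduled and unscheduled data are listed by subject, the groupings are shown by arm at each visit, and suicidal events reported as adverse events up to 14 days after the last dose appear in the treatment-emergent tables. In the 1, 1, 1 example, three listing lines settle the matter. Suicidality is also not among the events of special interest in protocol 7.1.4, and no hypothesis test depends on it. All of this stands, and it limits the weight of the point. But a listing is not a count per arm, and adverse event tables do not replace the instrument named as an endpoint.

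Four stronger readings are tempting, and the documents do not support them.

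- A reader might infer that the 0169 completers have no C-SSRS baseline. Only the lifetime and 12-month form is left unsummarized for them. Table 3 defines open-label and randomized-withdrawal baselines without restriction to De Novo subjects, although the latter is an interval form taken before the first randomized dose.
- A reader might infer that new cases cannot be told from old ones in about two thirds of subjects, since 170/258 = 66%. That ratio sets anticipated completers against planned open-label enrollment, not the randomized group. Exclusion criterion 20 also bars De Novo subjects with lifetime ideation or behavior, and SAP 4.1 says De Novo eligibility matches Study 0169, so positive histories should be uncommon.
- A reader might take protocol 8.6 as a promise of a whole-period C-SSRS table. The sentence concerns unscheduled categorical data only.
- A reader might say that SAP 9.7 excludes V10. Its wording covers every visit with a form; the loss comes from the windows in 6.5, whose two copies disagree.

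**Conclusion.** The point holds in limited form. As written, the SAP yields no table of distinct subjects per arm with any suicidal ideation, any behavior, or either over the randomized withdrawal period. Its record-selection rules can also remove a positive form that is the only evidence for its interval. The size depends on the data: for counts of one per visit, the ambiguity is 1 to 3 subjects in a planned arm of 77, before any discarded forms. This assumes that 6.5.1 applies to C-SSRS. No exception is stated; the special C-SSRS provision in 6.5 concerns only forms taken before the first open-label dose.

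The efficacy conclusions are untouched and the underlying data survive in listings. The change is worth making because the endpoint serves a primary objective and the repair is small.

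**What to change.** In SAP 9.7 add, for each treatment period and each arm or column of SAP 6.1, the number and percentage of distinct subjects with any ideation (1–5), any behavior (6–10), and either, at any post-baseline assessment. State that unscheduled, early-termination and V10 forms count and that these rows are exempt from the one-record-per-window rule. This also gives the unscheduled data of protocol 8.6 a place to go.

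In SAP 6.5 reconcile the EOS and EOT ends of the Week 22 window. Show V10 in its own row with its own denominator, since only subjects who do not enter Study 0171 attend it. If entry to 0171 differs by arm, follow-up differs too, so give the period count with and without V10.

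Optionally, add the number of subjects whose worst post-baseline category exceeds the pre-treatment one, taking the Study 0169 Baseline/Screening form for completers, as SAP 6.3.1 already does for norepinephrine. Given exclusion criterion 20 this should add little. It would first require reconciling protocol 6.4.10.1 (that form at V1) with SAP 9.7 (that form at screening, De Novo only).

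The cost is SAP wording and one table block from data already collected. The optional count also needs an import of the Study 0169 C-SSRS baseline.

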Appendix 2-9

	Protocol: 0170												
	Date of Assessment (DDMMYYYY)					Time of Assessment (24-hour clock)							
Visit						Subject ID Number					Rater Initials		
	1	7	0	-									

PATIENT GLOBAL IMPRESSION SEVERITY (PGI-S)

Please choose the response below that best describes the overall severity of your neurogenic orthostatic hypotension symptoms **over the past week**

- None
- Mild
- Moderate
- Severe
- Very severe

SAMPLE NOT TO BE USED

Appendix 2-10

	Protocol: 0170																	
	Date of Assessment (DDMMYYYY)						Time of Assessment (24-hour clock)											
									:									
Visit	Subject ID Number											Rater Initials						
	1	7	0	-									-					

PART I. MENTATION, BEHAVIOR AND MOOD (RATE ITEMS 1 TO 4 BY INTERVIEW)

1. Intellectual Impairment
 0 = None
 1 = Mild. Consistent forgetfulness with partial recollection of events and no other difficulties.
 2 = Moderate memory loss, with disorientation and moderate difficulty handling complex problems. Mild but definite impairment of function at home with need of occasional prompting.
 3 = Severe memory loss with disorientation for time and often to place. Severe impairment in handling problems.
 4 = Severe memory loss with orientation preserved to person only. Unable to make judgments or solve problems. Requires much help with personal care. Cannot be left alone at all.

Score:

2. Thought Disorder (Due to dementia or drug intoxication)
 0 = None
 1 = Vivid dreaming.
 2 = "Benign" hallucinations with insight retained.
 3 = Occasional to frequent hallucinations or delusions; without insight; could interfere with daily activities.
 4 = Persistent hallucinations, delusions, or florid psychosis. Not able to care for self.

Score:

3. Depression
 0 = Not present.
 1 = Periods of sadness or guilt greater than normal, never sustained for days or weeks.
 2 = Sustained depression (1 week or more).
 3 = Sustained depression with vegetative symptoms (insomnia, anorexia, weight loss, loss of interest).
 4 = Sustained depression with vegetative symptoms and suicidal thoughts or intent.

Score:

4. Motivation / Initiative
 0 = Normal
 1 = Less assertive than usual; more passive.
 2 = Loss of initiative or disinterest in elective (nonroutine) activities.
 3 = Loss of initiative or disinterest in day to day (routine) activities.
 4 = Withdrawn, complete loss of motivation.

Score:

ENTER TOTAL SCORE for PART I. MENTATION, BEHAVIOR AND MOOD: Total score:
 (from items 1 to 4 - maximum score = 16)

Protocol: 0170															
Visit	Subject ID Number											Rater Initials			
	1	7	0	-											

PART II. ACTIVITIES OF DAILY LIVING (RATE ITEMS 5 TO 17 BY INTERVIEW)

5. Speech
 0 = Normal.
 1 = Mildly affected. No difficulty being understood.
 2 = Moderately affected. Sometimes asked to repeat statements.
 3 = Severely affected. Frequently asked to repeat statements.
 4 = Unintelligible most of the time.

Score:

6. Salivation
 0 = Normal
 1 = Slight but definite excess of saliva in mouth; may have nighttime drooling.
 2 = Moderately excessive saliva; may have minimal drooling.
 3 = Marked excess of saliva with some drooling.
 4 = Marked drooling, requires constant tissue or handkerchief.

Score:

7. Swallowing
 0 = Normal.
 1 = Rare choking.
 2 = Occasional choking.
 3 = Requires soft food.
 4 = Requires NG tube or gastrostomy feeding.

Score:

8. Handwriting
 0 = Normal.
 1 = Slightly slow or small.
 2 = Moderately slow or small; all words are legible.
 3 = Severely affected; not all words are legible.
 4 = The majority of words are not legible.

Score:

9. Cutting food and handling utensils
 0 = Normal.
 1 = Somewhat slow and clumsy, but no help needed.
 2 = Can cut most foods, although clumsy and slow; some help needed.
 3 = Food must be cut by someone, but can still feed slowly.
 4 = Needs to be fed.

Score:

10. Dressing
 0 = Normal.
 1 = Somewhat slow, but no help needed.
 2 = Occasional assistance with buttoning, getting arms in sleeves.
 3 = Considerable help required, but can do some things alone.
 4 = Helpless.

Score:

11. Hygiene
 0 = Normal.
 1 = Somewhat slow, but no help needed.
 2 = Needs help to shower or bathe; or very slow in hygienic care.
 3 = Requires assistance for washing, brushing teeth, combing hair, going to bathroom.
 4 = Foley catheter or other mechanical aids.

Score:

Protocol: 0170														
Visit	Subject ID Number										Rater Initials			
	1	7	0	-										

PART II. ACTIVITIES OF DAILY LIVING

12. Turning in bed and adjusting bed clothes

- 0 = Normal.
- 1 = Somewhat slow and clumsy, but no help needed.
- 2 = Can turn alone or adjust sheets, but with great difficulty.
- 3 = Can initiate, but not turn or adjust sheets alone.
- 4 = Helpless.

Score:

13. Falling (unrelated to freezing)

- 0 = None.
- 1 = Rare falling.
- 2 = Occasionally falls, less than once per day.
- 3 = Falls an average of once daily.
- 4 = Falls more than once daily.

Score:

14. Freezing when walking

- 0 = None.
- 1 = Rare freezing when walking; may have start-hesitation.
- 2 = Occasional freezing when walking.
- 3 = Frequent freezing. Occasionally falls from freezing.
- 4 = Frequent falls from freezing.

Score:

15. Walking

- 0 = Normal.
- 1 = Mild difficulty. May not swing arms or may tend to drag leg.
- 2 = Moderate difficulty, but requires little or no assistance.
- 3 = Severe disturbance of walking, requiring assistance.
- 4 = Cannot walk at all, even with assistance.

Score:

16. Tremor

- 0 = Absent.
- 1 = Slight and infrequently present.
- 2 = Moderate; bothersome to patient.
- 3 = Severe; interferes with many activities.
- 4 = Marked; interferes with most activities.

Score:

17. Sensory complaints related to parkinsonism

- 0 = None.
- 1 = Occasionally has numbness, tingling, or mild aching.
- 2 = Frequently has numbness, tingling, or aching; not distressing.
- 3 = Frequent painful sensations.
- 4 = Excruciating pain.

Score:

ENTER TOTAL SCORE for PART II. ACTIVITIES OF DAILY LIVING:

(from items 5 to 17 - maximum score = 52)

Total score:

Protocol: 0170														
Visit	Subject ID Number										Rater Initials			
	1	7	0	-						-				

PART III MOTOR EXAMINATION (Acceptable responses are 0, 1, 2, 3, 4)

Please perform full UPDRS approximately 1 to 3 hours after the subject has taken a scheduled dose of their Parkinson's medication, preferably their morning dose). UPDRS in the ON state will be measured at a time representative of the ON state in that subject, not in "best" ON.

18. Speech
 0 = Normal.
 1 = Slight loss of expression, diction and/or volume.
 2 = Monotone, slurred but understandable; moderately impaired.
 3 = Marked impairment, difficult to understand.
 4 = Unintelligible.
 Score:

19. Facial Expression
 0 = Normal.
 1 = Minimal hypomimia, could be normal "Poker Face".
 2 = Slight but definitely abnormal diminution of facial expression.
 3 = Moderate hypomimia; lips parted some of the time.
 4 = Masked or fixed facies with severe or complete loss of facial expression; lips parted 1/4 inch or more.
 Score:

20. Tremor at rest
 Face, lips, chin + Right hand + Left hand + Right foot + Left foot =
 Score:
 0 = Absent.
 1 = Slight and infrequently present.
 2 = Mild in amplitude and persistent. Or moderate in amplitude, but only intermittently present.
 3 = Moderate in amplitude and present most of the time.
 4 = Marked in amplitude and present most of the time.

21. Action or Postural Tremor of hands
 Right hand + Left hand =
 Score:
 0 = Absent.
 1 = Slight; present with action.
 2 = Moderate in amplitude, present with action.
 3 = Moderate in amplitude with posture holding as well as action.
 4 = Marked in amplitude, interferes with feeding.

22. Rigidity (Judged on passive movement of major joints with subject relaxed in sitting position. Cogwheeling to be ignored.)
 Neck + RUE + LUE + RLE + LLE =
 Score:
 0 = Absent.
 1 = Slight or detectable only when activated by mirror or other movements.
 2 = Mild to moderate.
 3 = Marked, but full range of motion easily achieved.
 4 = Severe, range of motion achieved with difficulty.

Protocol: 0170														
Visit	Subject ID Number										Rater Initials			
	1	7	0	-						-				

PART III. MOTOR EXAMINATION

23. Finger Taps (Subject taps thumb with index finger in rapid succession with widest amplitude possible, each hand separately.)

Right hand + Left hand = Score:

- 0 = Normal.
- 1 = Mild slowing and/or reduction in amplitude.
- 2 = Moderately impaired. Definite and early fatiguing. May have occasional arrests in movement.
- 3 = Severely impaired. Frequent hesitation in initiating movements or arrests in ongoing movement.
- 4 = Can barely perform the task.

24. Hand Movements (Subject opens and closes hands in rapid succession with widest amplitude possible, each hand separately.)

[figure not shown]
Right hand + Left hand = Score:

- 0 = Normal.
- 1 = Mild slowing and/or reduction in amplitude.
- 2 = Moderately impaired. Definite and early fatiguing. May have occasional arrests in movement.
- 3 = Severely impaired. Frequent hesitation in initiating movements or arrests in ongoing movement.
- 4 = Can barely perform the task.

25. Rapid Alternating Movements of Hands (Pronation-supination movements of hands, vertically or horizontally, with as large an amplitude as possible, both hands simultaneously.)

Right hand + Left hand = Score:

- 0 = Normal.
- 1 = Mild slowing and/or reduction in amplitude.
- 2 = Moderately impaired. Definite and early fatiguing. May have occasional arrests in movement.
- 3 = Severely impaired. Frequent hesitation in initiating movements or arrests in ongoing movement.
- 4 = Can barely perform the task.

Protocol: 0170												
Visit	Subject ID Number										Rater Initials	
	1	7	0	-								

PART III. MOTOR EXAMINATION

23. Finger Taps (Subject taps thumb with index finger in rapid succession with widest amplitude possible, each hand separately.)

Right hand + Left hand = Score:

- 0 = Normal.
- 1 = Mild slowing and/or reduction in amplitude.
- 2 = Moderately impaired. Definite and early fatiguing. May have occasional arrests in movement.
- 3 = Severely impaired. Frequent hesitation in initiating movements or arrests in ongoing movement.
- 4 = Can barely perform the task.

24. Hand Movements (Subject opens and closes hands in rapid succession with widest amplitude possible, each hand separately.)

Right hand + Left hand = Score:

- 0 = Normal.
- 1 = Mild slowing and/or reduction in amplitude.
- 2 = Moderately impaired. Definite and early fatiguing. May have occasional arrests in movement.
- 3 = Severely impaired. Frequent hesitation in initiating movements or arrests in ongoing movement.
- 4 = Can barely perform the task.

25. Rapid Alternating Movements of Hands (Pronation-supination movements of hands, vertically or horizontally, with as large an amplitude as possible, both hands simultaneously.)

Right hand + Left hand = Score:

- 0 = Normal.
- 1 = Mild slowing and/or reduction in amplitude.
- 2 = Moderately impaired. Definite and early fatiguing. May have occasional arrests in movement.
- 3 = Severely impaired. Frequent hesitation in initiating movements or arrests in ongoing movement.
- 4 = Can barely perform the task.

26. Leg Agility (Subject taps heel on the ground in rapid succession picking up entire leg. Amplitude should be about 3 inches)

Right leg + Left leg = Score:

- 0 = Normal.
- 1 = Mild slowing and/or reduction in amplitude.
- 2 = Moderately impaired. Definite and early fatiguing. May have occasional arrests in movement.
- 3 = Severely impaired. Frequent hesitation in initiating movements or arrests in ongoing movement.
- 4 = Can barely perform the task.

27. Arising from Chair (Subject attempts to arise from a straight-back wood or metal chair with arms folded across chest.)

0 = Normal. Score:

- 1 = Slow; or may need more than one attempt.
- 2 = Pushes self up from arms of seat.
- 3 = Tends to fall back and may have to try more than one time, but can get up without help.
- 4 = Unable to arise without help.

28. Posture

0 = Normal erect. Score:

- 1 = Not quite erect, slightly stooped posture; could be normal for older person.
- 2 = Moderately stooped posture, definitely abnormal; can be slightly leaning to one side.
- 3 = Severely stooped posture with kyphosis; can be moderately leaning to one side.
- 4 = Marked flexion with extreme abnormality of posture.

Protocol: 0170													
Visit	Subject ID Number											Rater Initials	
	1	7	0	-									

PART III. MOTOR EXAMINATION

29. Gait
 0 = Normal
 1 = Walks slowly, may shuffle with short steps, but no festination or propulsion.
 2 = Walks with difficulty, but requires little or no assistance; may have some festination, short steps, or propulsion.
 3 = Severe disturbance of gait, requiring assistance.
 4 = Cannot walk at all, even with assistance.

Score:

30. Postural Stability (Response to sudden, strong posterior displacement produced by pull on shoulders while subject is erect, with eyes open and feet slightly apart. Subject is prepared.)
 0 = Normal.
 1 = Retropulsion, but recovers unaided.
 2 = Absence of postural response; would fall if not caught by examiner.
 3 = Very unstable, tends to lose balance spontaneously.
 4 = Unable to stand without assistance.

Score:

31. Body Bradykinesia and Hypokinesia (Combining slowness, hesitancy, decreased arm swing, small amplitude and poverty of movement in general)
 0 = None.
 1 = Minimal slowness, giving movement a deliberate character; could be normal for some persons. Possibly reduced amplitude.
 2 = Mild degree of slowness and poverty of movement which is definitely abnormal. Alternatively, some reduced amplitude.
 3 = Moderate slowness, poverty or small amplitude of movement.
 4 = Marked slowness, poverty or small amplitude of movement.

Score:

A. Indicate the subject's PD state during the examination (check one):

- "On" during exam
- Fluctuated during the exam
- "Off" during exam

ENTER TOTAL SCORE for PART III. MOTOR EXAMINATION: Total score:
 (from items 18 to 31 - maximum score = 108)

Protocol: 0170															
Visit	Subject ID Number											Rater Initials			
	1	7	0	-							-				

PART IV. COMPLICATIONS OF THERAPY (In the past week)

A. DYSKINESIAS

32. Duration: What proportion of the waking day are dyskinesias present?
 (Historical information.)

0 = None
 1 = 1-25% of day
 2 = 26-50% of day
 3 = 51-75% of day
 4 = 76-100% of day

Score:

33. Disability: How disabling are the dyskinesias? (Historical information; may be modified by office examination.)

0 = Not disabling.
 1 = Mildly disabling.
 2 = Moderately disabling.
 3 = Severely disabling.
 4 = Completely disabled.

Score:

34. Painful Dyskinesias: How painful are the dyskinesias?

0 = No painful dyskinesias.
 1 = Slight.
 2 = Moderate.
 3 = Severe.
 4 = Marked.

Score:

35. Presence of Early Morning Dystonia (Historical information.)

0 = No
 1 = Yes

Score:

ENTER TOTAL SCORE for PART IV. A. Dyskinesias (from items 32 to 35 - maximum score = 13)

Total score:

SAMPLE NOT TO BE USED

Protocol: 0170															
Visit	Subject ID Number											Rater Initials			
	1	7	0	-											

PART IV. COMPLICATIONS OF THERAPY (In the past week)

B. CLINICAL FLUCTUATIONS

36. Are any "off" periods predictable as to timing after a dose of medication?
 0 = No
 1 = Yes
 Score:

37. Are any "off" periods unpredictable as to timing after a dose of medication?
 0 = No
 1 = Yes
 Score:

38. Do any of the "off" periods come on suddenly, e.g. over a few seconds?
 0 = No
 1 = Yes
 Score:

39. What proportion of the waking day is the subject "off" on average?
 0 = None
 1 = 1-25% of day
 2 = 26-50% of day
 3 = 51-75% of day
 4 = 76-100% of day
 Score:

ENTER TOTAL SCORE for PART IV. B. Clinical Fluctuations Total score:
 (from items 36 to 39 - maximum score = 7)

C. OTHER COMPLICATIONS

40. Does the subject have anorexia, nausea, or vomiting?
 0 = No
 1 = Yes
 Score:

41. Does the subject have any sleep disturbances, e.g. insomnia or hypersomnolence?
 0 = No
 1 = Yes
 Score:

42. Does the subject have symptomatic orthostasis?
 0 = No
 1 = Yes
 Score:

ENTER TOTAL SCORE for PART IV. C. Other Complications Total score:
 (from items 40 to 42 - maximum score = 3)

Protocol: 0170												
Visit	Subject ID Number										Rater Initials	
	1	7	0	-								

Part V. MODIFIED HOEHN AND YAHR STAGING

- Stage 0 = No signs of disease.
- Stage 1 = Unilateral disease.
- Stage 1.5= Unilateral plus axial involvement.
- Stage 2 = Bilateral disease, without impairment of balance.
- Stage 2.5= Mild bilateral disease, with recovery on pull test.
- Stage 3 = Mild to moderate bilateral disease; some postural instability; physically independent.
- Stage 4 = Severe disability; still able to walk or stand unassisted
- Stage 5 = Wheelchair bound or bedridden unless aided.

Part VI. MODIFIED SCHWAB AND ENGLAND ACTIVITIES ON DAILY LIVING SCALE

- 100%- Completely independent. Able to do all chores without slowness, difficulty or impairment. Essentially normal. Unaware of any difficulty.
- 90%- Completely independent. Able to do all chores with some degree of slowness, difficulty, and impairment. Might take twice as long. Beginning to be aware of difficulty.
- 80%- Completely independent in most chores. Takes twice as long. Conscious of difficulty and slowness.
- 70%- Not completely independent. More difficulty with some chores. Three to four times as long in some. Must spend a large part of the day with chores.
- 60%- Some dependency. Can do most chores, but exceedingly slowly and with much effort. Errors; some impossible.
- 50%- More dependent. Help with half, slower, etc. Difficulty with everything.
- 40%- Very dependent. Can assist with all chores, but few alone.
- 30%- With effort, now and then does a few chores alone or begins alone. Much help needed.
- 20%- Nothing alone. Can be a slight help with some chores. Severe invalid.
- 10%- Totally dependent, helpless. Complete invalid. 0%-Vegetative functions such as swallowing, bladder, and bowel functions are not functioning. Bedridden.

